De-identified sonographic pictures will be obtained by a trained healthcare provider (physician, midwife, nurse practitioner, nurse) from the site for each test location of the optical sensor. The de-identified image will be uploaded to the database which is a secure web application for building and managing online surveys and databases. The study team will take every precaution to ensure that the image is completely free of identifiers.

A single de-identified photograph showing the position of the sensor for each test location on the maternal abdomen may be obtained on a stylized image. This image will be uploaded to the database which is a secure web application for building and managing online surveys and databases. The study team will take every precaution to ensure that the image does not capture any identifiable portion of the patient. All data will be de-identified prior to data entry in the database.

To verify accuracy of the LUMERAH algorithm for laboring women, as derived from experimental studies in the pregnant ovine model, Raydiant Oximetry will use a Nellcor N-400 system with a sterile internal sensor (manufactured by Axcesor) in all subjects. The internal sensor will be placed *after* rupture of membranes (amniotic sac) and the fetus has descended to at least a -2 station. The sensor will be placed by a trained healthcare provider (physician, midwife, nurse practitioner, nurse) and the placement confirmed before initiation of LUMERAH data collection. The data collection plan is to obtain approximately 40 data sets on each of the laboring patients. Each data set takes 90-120 seconds to gather (~ 2-3 hours in total), and a pre/post ground truth assessment will be obtained for each data set. It is anticipated that subjects will participate for a minimum of 10 minutes (where only a few data sets are obtained) but for no more than 6 hours. The obstetric provider will be blinded to both the LUMERAH data and the internal sensor data.

VERSION DATE: 9/8/21

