The device shipments/delivery and request for return will be the responsibility of the Sponsor. The device is not delivered to the site until IRB approval has been obtained. The Investigational device is precommercialization and will not be available to study subjects after participation in the study. Study subjects will not be restricted from use of any medication or other substance while participating in the study. In addition to the PI and co-investigators, members of the Raydiant Oximetry team may transport and be accountable for the investigational device.

10. Data Collection

In addition to specific LUMERAH device and cardiotocography data, the following data is the minimum subject data set to be collected during this study:

- Maternal demographics such as race, ethnicity, age, parity, prior perinatal outcomes, height, weight (to calculate BMI), number and date of prior cesarean deliveries, Maternal Vital Signs such as the maternal heart rate and maternal oxygen saturation.
- CTG Tracings to be downloaded from the EMR
- Location on maternal abdomen for best signal quality
- Safety data (see "Adverse Event Reporting" below)

In addition, the internal sensor data will be analyzed and compared to the LUMERAH device data. We will report the mean error, standard deviation of difference and root-mean square error from the study results. In addition, we will present a scatter plot (with the identity line and Deming regression line), a Bland-Altman plot [with the 95% limits of agreement (LoA)] and report the repeatability and reproducibility by providing a population mean bias (μ 0), between-subject variance (σ 2) with our final statistical analyses.

Neonatal outcomes will not be collected during this study.

11. Risks to Subjects/NSR Determination

A significant-risk (SR) device study is defined by the United States Food and Drug Administration (https://www.fda.gov/media/75459/download) as one that:

- Is intended as an implant and presents a potential for serious risk to the health, safety, or welfare of a subject;
- Is purported or represented to be for use supporting or sustaining human life and presents a potential for serious risk to the health, safety, or welfare of a subject;
- Is for a use of substantial importance in diagnosing, curing, mitigating, or treating disease, or otherwise preventing impairment of human health and presents a potential for serious risk to the health, safety, or welfare of a subject;

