This is an observational, noninvasive study with primary endpoints related to the LUMERAH device correlation with the Nellcor device and internal sensor (manufactured by Axcesor). Raydiant Oximetry met with the FDA on Feb 11, 2020 and suggested that we power our pilot and pivotal studies for specificity, and not sensitivity, because poor specificity of CTG technology is the unmet clinical need in obstetrics. CTG technology has a 29% specificity and the FDA agreed with this approach. Seelbach-Gobel²³ demonstrated that the Nellcor fetal pulse oximetry device had a specificity of 65% for the detection of newborn metabolic acidosis. The incidence of newborn metabolic acidosis has been reported to be 2-4% and the incidence of hypoxic fetuses is 3-4%. Our sample size calculations are based on a significance level of 0.05 (i.e. type 1 error=0.05) with the goal to achieve power of 0.8 and a lower confidence level of 80% to establish a clinical proof of concept. The sample size calculation, under these assumptions, is 48 subjects for this pilot study.

VERSION DATE: 9/8/21

To compare the Nellcor N-400 device output to the LUMERAH output, we are following the FDA guidance document (dated March 4, 2013) for pulse oximeters, where the in-vivo validation set should include at least 200 data points from 10 or more human subjects. Per the FDA recommendation, we will report the root mean square (RMS) error and produce a scatter plot with the identity line and a Deming regression line. In addition, we will report a Bland-Altman plot with the 95% limits of agreement as well as the 95% confidence intervals for the limits of agreement.

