Our preclinical data set for algorithm training required approximatively 300 data points from 20 sheep. We expect that a similar amount of human data sets will be required for algorithm training and then another 10 human subjects will be enrolled for prospective algorithm validation of the LUMERAH device. Therefore, the absolute *minimum* required sample size to compare Nellcor N-400 device output to the LUMERAH output is 30 subjects. However, we will calibrate and validate on up to 60 patients to ensure that we can identify hypoxic fetuses. East et al²⁴ reported that 3.9% of observations with the Nellcor N-400 technology displayed fetal oxygen saturations below 30%. Therefore, enrolling and following 60 subjects allows the opportunity to monitor and study approximately two hypoxic fetuses. We intend to collect up to 60 of these "ground truth" cases with varied oxygenation levels before proceeding to PILOT 2. With the expectation that we will have to consent an additional 50% who may not meet the inclusion/exclusion criteria, the total number consented will be a maximum of 90 subjects.

17. Data Management

Only individuals approved by the Sponsor and who have adequate training in the use of the Investigational device are given authorization of access to perform the measurement and record the data. The data collected will be marked with a study ID number to protect confidentiality of each subject.

Only the research staff will have access to the link between the study ID and the patient's identifying information. The key will be stored in a password-protected document on a restricted access folder on the hospital network. Only the PI/Co-I and research team will have access to this document.

A separate document listing only study ID numbers will be stored on a password-protected document on a restricted access folder on the hospital network. This will contain the subjects' de-identified obstetric and medical history as relevant for the project. Data will be submitted to the sponsor through an electronic, secure database.

18. Study Monitoring

This study will be monitored for data accuracy and adherence to the protocol by the Sponsor's representative and/or a 3rd party qualified monitor. It is expected that there will be frequent attendance of the Sponsor's representative at the study site. Major protocol deviations will be reported to the Sponsor immediately and the IRB at the required reporting intervals.

19. Regulatory Requirements

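### Sixty subjects do not ensure that a hypoxic fetus is seen (9–16% chance of none at the protocol's own incidence), and no planned error figure is given for saturations below 30%

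*Combined protocol and SAP*

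**What the plan says.** Section 16 sets 30 subjects as the absolute minimum for comparing the two devices: about 20 for algorithm training, by analogy with the sheep work, and 10 for prospective validation. It then gives its reason for going higher: "However, we will calibrate and validate on up to 60 patients to ensure that we can identify hypoxic fetuses".

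Two sentences later the claim is milder. After citing a study in which "3.9% of observations with the Nellcor N-400 technology displayed fetal oxygen saturations below 30" per cent, the section concludes that "enrolling and following 60 subjects allows the opportunity to monitor and study approximately two hypoxic fetuses". Earlier in the same section a rate per fetus is given: "the incidence of hypoxic fetuses is 3-4" per cent. No chance of seeing at least one hypoxic fetus is stated, and no minimum number of such cases is set.

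On agreement, Section 10 says: "We will report the mean error, standard deviation of difference and root-mean square error from the study results". It adds a scatter plot with identity and Deming lines, a Bland-Altman plot, a population mean bias and a between-subject variance. Section 16 repeats the RMS error and the scatter plot, and says "we will report a Bland-Altman plot with the 95% limits of agreement", with confidence intervals for those limits. None of these is specified for any part of the saturation range.

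**The concern.** Two things do not fit together.

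First, the step from 30 to 60 subjects rests on a guarantee, and an expected count of about two does not guarantee any. A sponsor or ethics committee reading that sentence would take it that the pilot is sized so that hypoxic fetuses will be among those studied.

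Second, the synopsis describes the device as an adjunct that detects falls in fetal oxygenation. Section 1 uses 30% saturation as the threshold for hypoxia, and Section 16 enlarges the sample for the sake of hypoxic fetuses. Yet every planned error figure averages over all saturations. If few readings are low, large errors below 30% could sit behind a satisfactory overall RMS error. Section 16 places this pilot ahead of PILOT 2, so this is the stage at which to show how much, or how little, was learned about the low range.

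**Working it through.** **Inputs**
- Sample size: n = 60, a ceiling (Section 16); stated minimum 30 (Section 16).
- Incidence of hypoxic fetuses: p = 0.03 to 0.04 per fetus (Section 16).
- Share of N-400 observations below 30% in the cited study: 0.039 (Section 16).
- Assumptions: fetuses are independent, and the 3–4% applies to the women enrolled.

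**The protocol's own figure.** 60 × 0.039 = 2.34. By the fetus-level rate, 60 × 0.03 = 1.8 and 60 × 0.04 = 2.4. Both routes give about two, so the stated count reproduces. The fetus-level rate is the safer basis, because a share of observations does not by itself fix a number of fetuses.

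**Chance of no hypoxic fetus**, (1 − p)^n:
- n = 60: 0.97^60 = 0.161; 0.96^60 = 0.086. That is 9–16%.
- n = 30: 0.97^30 = 0.401; 0.96^30 = 0.294. That is 29–40%.

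**Chance of two or more at n = 60**, 1 − (1 − p)^60 − 60p(1 − p)^59:
- p = 0.03: 1 − 0.161 − 0.298 = 0.541.
- p = 0.04: 1 − 0.086 − 0.216 = 0.698.

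**Subjects needed for a chance of none of 5% or less**, ln(0.05)/ln(1 − p):
- p = 0.03: 98.4, so 99.
- p = 0.04: 73.4, so 74.

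Going from 30 to 60 therefore helps a good deal, but it does not bring the chance of none to 5%.

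**What a pooled RMS error would show.** This is an illustration only. It takes 3.9% of readings below 30% as carrying over from the cited study, and assumes an RMS error of 5 points at or above 30% and of 10 or 15 points below:
- 10 points: √(0.961 × 25 + 0.039 × 100) = √27.93 = 5.28.
- 15 points: √(0.961 × 25 + 0.039 × 225) = √32.80 = 5.73.

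Error two or three times as large in the low range moves the overall figure from 5 to 5.3 or 5.7.

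**The case against.** The strongest reply is that Section 16 corrects itself: it discloses an expected count of about two and speaks of an opportunity, and *to ensure* can be read as a statement of purpose. That largely stands. The wording point is a one-phrase edit, and it matters mainly because that phrase is the reason given for enlarging the sample.

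A second reply is that the result depends on what counts as hypoxic. Section 16 does not define the condition behind its 3–4%, while its count of two is derived from readings below 30%. If 3.9% of readings are low but only half, or a quarter, of an affected fetus's readings are low (both assumed), the affected share is 0.039/0.5 = 7.8% or 0.039/0.25 = 15.6%. The chance of no affected fetus in 60 is then 0.922^60 = 0.8%, or 0.844^60, below 0.1%. Section 1's description, below 30% for 10 minutes, points to a stricter definition, so the matter is open. A reader might infer from the 9–16% that the pilot has that chance of yielding no reading below 30%. The documents do not support that inference, and the figure is not evidence for or against the separate table proposed here.

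A third reply is that the agreement outputs follow the FDA pulse-oximeter guidance the protocol names, that power was directed to specificity, and that no accuracy claim below 30% is planned. This is fair. Nor is the low range invisible: both plots show it, and the Deming line, fitted across the range, can reveal bias that changes with level. But the protocol does not promise the line's coefficients, few low readings would inform it, and no error figure for the low range follows from any of these.

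**Conclusion.** The point holds in two limited parts.

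- **Sample-size wording.** At the stated 3–4% incidence, with independent fetuses and the full 60 enrolled, 1.8–2.4 hypoxic fetuses are expected, with a 9–16% chance of none and a 54–70% chance of two or more. The estimate of about two and the language of opportunity are right; *ensure* is not. With fewer than 60 subjects the chance of none rises. The exclusion of Category III tracings at entry could make the true rate differ from the one quoted.
- **Reporting.** No numerical agreement summary separates readings below the protocol's own 30% threshold. If about 4% of readings are low, which is carried over from the cited study, pooled figures would barely reflect error there.

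A reader might go further and infer that the pilot is too small or needs more subjects. The documents do not support that: Section 16 sets no target number of hypoxic cases, and the 48-subject specificity calculation is a separate matter on which this point does not depend. The reporting change is the more useful of the two, and the restatement is a minor companion to it.

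**What to change.** 1. **Section 16.** Replace the sentence containing *ensure* with wording such as: *sixty subjects give the opportunity to study about two hypoxic fetuses (expected 1.8–2.4 at an incidence of 3–4%; chance of none 9–16%)*. Cite the fetus-level incidence as the basis. Do not present the 9–16% as the chance that no reading falls below 30%.
2. **Sections 10 and 16.** In addition to the pooled summaries, report mean error and RMS error separately for Nellcor readings below 30% and at or above 30%. Give the number of readings and of subjects in each group, and identify which come from validation subjects.
3. **Interpretation rule, stated in advance.** If the low group is empty or comes from only one or two fetuses, describe it only and state that accuracy below 30% was not established.

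The cost is a sentence and one descriptive table from data already being collected. The low-range cells will be sparse. Because the groups are formed on the Nellcor reading, some values will be in the low group through Nellcor error alone, so some apparent overestimation by LUMERAH below 30% is to be expected; the table should carry a note saying so. The statement of what the pilot can show about hypoxia also becomes less favourable.

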20.1 Principal investigator responsibilities

- a) Permit Sponsor/Monitor inspection of facilities and records.
- b) Permit inspection of facilities and records by government bodies.
- c) Submit protocol and informed consent to IRB and await approval.
- d) Submit proposed amendments to protocol and informed consent to IRB and await approval, unless the change reduces the risk to subjects.
- e) Obtain informed consent of subjects.
- f) Implement study in accordance with protocol.
- g) Complete case report forms.
- h) Explain deviations from protocol and report to monitor.
- i) Submit annual progress reports, final reports, and adverse effect reports to IRB and Sponsor as required by law.
- j) Record the receipt, disposition, and return of devices.
- k) Retain records for a minimum of two years following study completion (refer to IRB rules).

